To address this problem, we developed a tablet application, called Pediatric Accurate Medication In Emergency Situations (PedAMINES). This app is a supportive tool designed to drive caregivers step-by-step and in real-time from preparation to delivery of a wide range of drugs, especially those required during resuscitation. We conducted a prior multicentric randomized controlled crossover trial granted by the *Swiss National Science Foundation* in 6 pediatric emergency departments in Switzerland during a simulation-based pediatric cardiac arrest scenario. Medication errors were reduced from 75.9% to 10.2% by using respectively conventional preparation methods or PedAMINES ($P < .0001$). While using PedAMINES time to drug preparation (TDP) and delivery (TDD) were reduced by 147.5 (48%) and 170.5 (39%) seconds respectively (both $P < .0001$). However, the app was not assessed in prehospital settings.

Objectives: we aim to determine whether the use of PedAMINES improves the management of acute pediatric prehospital life-threatening conditions in Switzerland by quickly delivering expertise in IV drugs administration and by avoiding medication errors. We hypothesize that PedAMINES will reduce medication errors, TDP and TDD independently of the existing conventional preparation methods used or EMS' skills.

Method: a multicenter, prospective, unblinded, randomized controlled trial to compare the efficacy of PedAMINES vs conventional methods in the preparation of IV emergency medications during a video-recorded simulation-based pediatric cardiac arrest scenario. **Participants:** 120 paramedics in several EMS all over Switzerland. **Randomization:** stratified on EMS and centralized with a 1:1 allocation ratio. The study is formatted according to the CONSORT-EHEALTH and the Reporting Guidelines for Health Care Simulation Research statements.

Intervention: each paramedic will be asked to prepare a standardized series of 4 IV emergency medications, using either PedAMINES (intervention group) or conventional methods (control group). Two questionnaires will be given before and after the scenario to collect paramedics' demographics data and satisfaction. Stress level will be assessed by questionnaire and heart rate will be recorded as a stress marker with a fitness watch.

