2.3.3. Study design

The study is a prospective, multicenter, randomized controlled trial with 2 parallel groups comparing PedAMINES^{46,47} with conventional precalculated drug dosing charts used by EMS in the preparation of direct IV drugs during a standardized simulation-based pediatric cardiac arrest scenario. The drug dosing charts is presented as a spreadsheet, enabling the preparation of the commonly ordered concentrations of emergency medications at varying dose ranges based on the patient's weight. To calculate the composition of the drug to inject, one first selects the desired drug dosage to be delivered in mg/kg. The next step is to calculate the milliliters of drug based on the weight of the patient to be diluted with compatible fluids (sodium chloride 0.9%, etc) in a syringe. For the purpose of the study, we will not select drugs that can be directly drawn from the vial without calculation and dilution.

The multicentric setting of the study will involve 15 Swiss EMS (Cantons of Geneva, Vaud, Neuchâtel, Fribourg, Jura, Zurich, Bern, Basel, Lucern, Ticino). To ensure optimal quality of reporting, the trial is formatted according to the Consolidated Standards of Reporting Trials Statement for Randomized Controlled Trials of Electronic and Mobile Health Applications and Online TeleHealth (CONSORT-EHEALTH)⁴⁸ and the Reporting Guidelines for Health Care Simulation Research⁴⁹

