On the day of participation, paramedics will complete a survey collecting data regarding their demographics, care training, and simulation and computer experience. After random allocation, each participating paramedic will receive a standardized 5-minute training session on how to use the PedAMINES app. Paramedics will remain unaware of drugs that will be used and specific endpoints of the study during this training session. The simulation manikin characteristics are then presented. The paramedics will then be asked to perform the pediatric resuscitation scenario. This scenario is standardized to follow the same chronological progression and range of difficulty to ensure each participant is exposed to exactly the same case, with similar challenges in decision making and treatment preparation provided on the same manikin. The uniform delivery of the scenario all along the study will minimize confounders. Study team members will only adapt to progression speed of participants through the scenario by maintaining a stressful resuscitation atmosphere. The scenario will be videorecorded and conducted in a simulated children room in each area in order to increase realism. High levels of realism are known to immerse participants in the simulated experience and prevent confounding

variables that might potentially affect the way individuals perform⁵⁰. The simulated room will be exclusively devoted to the simulation to prevent unexpected interruption or external stimuli. Portable monitoring alarms will be activated to increase realism and stress. All usual EMS resuscitation equipment will be at the disposal of the paramedic. In both allocation groups, the decision to use or not use any equipment will remain personal as in real life. Neither pilot testing nor repetitions will be permitted. There will be neither interventions nor educational adjuncts prior to or after the study period. Once the experiment completed, the paramedic will be required to recall and describe precisely how he prepared the drugs in order to verify that the drug names and original doses prescribed by the physician were correctly understood to assess the presence of comprehension bias.

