Resuscitation scenario: the untimed portion of the simulation starts by turning on the video cameras and the fitness watch. The paramedic and both investigators (the confederate paramedic and the physician) wait outside the room where they are supposedly dispatched. The team will be invited to enter the room by the father (simulated by the technician operating the manikin). A clinical statement to recognize the life-threatening condition of the patient, including his weight and age, is then given by the father as follows: "Here is Junior, a 12-kg, 1 and a half year old boy who suddenly collapsed 15 minutes ago. Oral tricyclic antidepressant as well as antidiabetic pills from his grandmother were found in his mouth and on the ground of his room. He is unconscious, pale and does not breathe". At this moment, the physician asks the participant to take a central pulse. Because of the invariable absence of a pulse, the latter is asked to assist the physician to perform a 2-min full course massage and ventilation (15:2 ratio) maneuver to increase his own stress level (massage carried out by the participant). During this time, the physician asks the confederate paramedic to place a 4-derivation electrocardiogram on the manikin, an upper arm blood pressure monitor, a digital pulse oximeter and defibrillator's patches. Then the physician asks to change roles; the confederate paramedic has to carry out the massage while the participant has to get a peripheral vascular access on the manikin's right hand. At this time, an asystole rhythm is recognized and verbalized by the physician. On the basis of the American Heart Association pediatric cardiac arrest algorithm for asystole⁴, a bolus of epinephrine is ordered by the physician and the timed scenario begins. The participant must prepare and administer the drug with the help of PedAMINES (intervention group) or following the conventional method. ROSC ensues with generalized tonic-clonic seizures. The physician says: "The patient has now a return of spontaneous circulation with a pulse but with seizures. This patient needs an IV bolus of midazolam right now". The seizures stop 15 seconds after administration of the drug. At this time the physician asks the participant to perform a finger stick to obtain a blood sample. The glucometer reports a blood sugar of 0.8 mmol/L. The physician says: "the patient has a severe

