2.3.5.3. Adherence

The study will take place during a 1-week period in each EMS and will occupy each paramedic for a single 60-minute period. Thanks to our experience gathered in previous studies, we anticipate a very low rate of drop-outs or loss of follow-up. To ensure the presence of participants on the day of participation, shift-working paramedics will be randomly recruited 1 month before the start of the study by a blinded noninvestigator. They will be informed of the upcoming simulation study but not of its purpose and outcomes. Each paramedic will be rewarded individually by an amount of 50.- CHF for its participation to the study. Adherence of the collaborating EMS to our study will be reinforced by their citation in further publications and by a privileged access to the PedAMINES app.

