2.3.5.4. Concomitant care

The paramedics will be allowed to use their current, conventional method of preparing direct IV drugs, even if it differs between EMS. This will avoid introducing evaluation bias on the baseline ability of paramedic to prepare drugs “as usual” if allocated in the group without PedAMINES. This will also test the absolute capacity of the app to reduce medication errors and drugs delays, indifferently of the prior traditional method used.

However, participants will not be allowed to use any other drug support device and the scenario will remain secret until it starts to avoid upstream drugs preparation's refresh.

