2.3.7. Patients Timeline

On-site staff in every collaborating EMS will organize participation of paramedics to the study. No information about the ongoing study will be given to the paramedics at this stage. The best study period will be matched with study coordinators. The paramedics will be spread throughout 1 week in order to link up the several scenarios. On scheduled weeks, the study coordinators will visit the collaborating EMS, provide trial information to participants before they begin the scenario, and assessment of eligibility will be verified. Participants will then sign the informed consent. They will be asked to complete an anonymised demographic questionnaire and confirm their willingness to participate. If it's the case, they will pursue with a 5-minute learning session to the use of PedAMINES given by the investigators. Then, each participant will be randomly allocated to study arms. Immediately after the randomization, the paramedic will start the scenario. 1) the overall stress perceived during the scenario and during each drug preparation, and 2) the satisfaction about the preparation method used. The total study period to enroll all paramedics in the various EMS will take 12 months.

Table 1. PedAMINES timeline protocol for forms and procedures

	Study Period				
	Pre-enrollment	Enrollment / consent	Pre-study baseline / allocation	20-minute scenario	Closeout
Time point	$-t_2$	$-t_1$	0	t_1	t_x
ENROLMENT:					
Invitation to participate	X				
Eligibility screen		X			
Informed consent form		X			
Demographic questionnaire			X		
PedAMINES learning session			X		
Randomization			X		
INTERVENTION :					
Group A (with PedAMINES)				X	
Group B (with conventional method)				X	
Termination questionnaire					X
ASSESSMENTS :					
Medication errors				X	
Time at prescription				X	
Time to drug preparation (TDP) and delivery (TDD)				X	

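### Colleagues at each EMS run the identical scenario in succession over one week, and nothing stops or records briefing of those still to come, so the measured effect may be diluted

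*Combined protocol and SAP*

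**What the plan says.** The scenario is fixed. Section 2.3.5.1 standardises it so that "each participant is exposed to exactly the same case", and the opening statement is always "Here is Junior, a 12-kg, 1 and a half year old boy". The order of drugs is also fixed: epinephrine, midazolam, dextrose 10%, sodium bicarbonate. The summary confirms that "each paramedic will be asked to prepare a standardized series of 4 IV emergency medications".

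The timing is set in two places. Section 2.3.5.3: "The study will take place during a 1-week period in each EMS". Section 2.3.7: "The paramedics will be spread throughout 1 week in order to link up the several scenarios". Section 2.3.3 adds that "The multicentric setting of the study will involve 15 Swiss EMS", and section 2.3.10.1 randomises individuals 1:1 within each centre, so both arms are present at each EMS.

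On secrecy, section 2.3.5.4 states that "the scenario will remain secret until it starts to avoid upstream drugs" are gone over again. The other safeguards also act before a participant's own run:

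- Purpose and outcomes are withheld at recruitment (2.3.5.3, 2.3.11.1).
- No study information is given while sessions are organised (2.3.7).
- The drugs and endpoints are withheld during app training (2.3.5.1).
- Pilot runs and repetitions are excluded (2.3.5.1).

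After the run, section 2.3.5.1 has participants describe how they prepared the drugs. The stated aim is to check that the physician's orders were understood.

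**The concern.** The plan itself treats advance refreshing of the drugs as a threat, but it protects each participant only from the study team's side. Once the first paramedic at an EMS has finished, that person knows the weight, the drugs and the order, and colleagues will face the same case within days. No section asks for silence, varies the case, asks later participants what they had heard, or records where in the week they fell. The models in section 2.3.14.1 adjust for type of medication and have no term for session order.

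A forewarned paramedic could look up or work out four volumes for 12 kg in advance. In the control arm that replaces the calculation described in section 2.3.3. In the app arm the calculation is already done for the user (section 2.2), so there is less to gain. If so, some controls would no longer show their usual ability, which section 2.3.5.4 sets out to preserve. The differences in dosing errors, TDP and TDD would then be underestimated, whatever the P value.

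**Working it through.** **Inputs from the documents.** Section 2.3.8: control error rate 60%, difference 30 points (so 30% with the app), two-sided alpha 0.05, power 90%, 56 per arm needed, 60 per arm recruited. Section 2.3.3: 15 EMS. Section 2.2: 10.2% errors with the app in the earlier in-hospital trial.

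**Inputs that I assume, because the documents give none.** The share q of later controls who are forewarned (10%, 20%, 30%), and the error rate e of forewarned controls (30%, 45%, 50%).

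**Step 1: reproduce the plan's figure.** Two-proportion formula with pooled variance under the null and no continuity correction, mean proportion 0.45:

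n = [1.960·√(2·0.45·0.55) + 1.2816·√(0.6·0.4 + 0.3·0.7)]² / 0.30² = (1.379 + 0.860)² / 0.09 = 55.7, so 56 per arm, as stated.

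Power at 60 per arm = Φ[(0.30 − 1.960·√(0.495/60)) / √(0.45/60)] = Φ(1.41) = 0.92.

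**Step 2: share exposed.** 120 / 15 = 8 per EMS on average, so 7 of 8 (87.5%) follow at least one colleague.

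**Step 3: diluted control rate.** Control rate = 0.60 − 0.875·q·(0.60 − e). For example, q = 30% and e = 30% give 0.60 − 0.875·0.30·0.30 = 0.521.

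| Error rate if forewarned (e) | q | Control rate | Difference, app at 30% | Power, 60 per arm |
|---|---|---|---|---|
| 30% | 10% | 57.4% | 27.4 | 87% |
| 30% | 20% | 54.8% | 24.8 | 79% |
| 30% | 30% | 52.1% | 22.1 | 70% |
| 45% | 10% | 58.7% | 28.7 | 90% |
| 45% | 20% | 57.4% | 27.4 | 87% |
| 45% | 30% | 56.1% | 26.1 | 83% |
| 50% | 10% | 59.1% | 29.1 | 90% |
| 50% | 20% | 58.3% | 28.3 | 89% |
| 50% | 30% | 57.4% | 27.4 | 87% |

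**Step 4: let the app arm vary.**

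- If forewarning halves the error rate in both arms, power is 90%, 87% and 84% for q = 10%, 20% and 30%.
- If both arms as a whole fall by the same 5 to 15 points, power does not fall (93–96%).
- If the app arm errs at 10.2%, power exceeds 99% in every row of the table.

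**Step 5: relation to the planned analysis.** The table treats each paramedic as one observation. Section 2.3.14.1 fits a mixed logistic model to four preparations per paramedic. As a rough guide, with an assumed within-paramedic correlation of 0.4 the design effect is 1 + 3·0.4 = 2.2, and the effective size is 240/2.2 = 109 per arm. The worst row (52.1% against 30%) then has power of about 92%. At a correlation of 0.6 (design effect 2.8, effective size 86) it is about 84%.

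**The case against.** A reader might infer that the plan lets secrecy lapse as soon as the first session begins. The text does not require that reading. Taken participant by participant, the rule means that nobody knows the case before their own run, and that would cover the whole week. The aim is then right; what is missing is any means of achieving it.

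A reader might also infer that only controls would benefit. That is inference. Allocation is concealed until the scenario starts (2.3.10.2), so nobody can rehearse as a control, and both arms could prepare. The plan withholds the drugs during app training, which suggests that foreknowledge could matter there too. TDP runs to a filled syringe, so handling counts in both arms. Nor would foreknowledge remove every control error: section 2.1 lists inaccurate measurement of volumes among the causes. What survives is that the calculation step can be done ahead by a control and is already done by the app, so a larger gain in controls is plausible.

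The most tempting inference is that the trial is left with 70% power. That figure needs 30% of later controls forewarned, each gaining the full 30 points, with no gain among app users and one observation per person. Milder assumptions give 83–90%. The documents fix none of these inputs.

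Finally, the post-scenario recall asks how the drugs were prepared, so advance preparation might surface there. It is not designed to find it, however, and nothing says that it would be recorded.

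**Conclusion.** The gap is real. The case is identical, colleagues follow one another within a week, and the plan neither prevents nor records briefing, although it names advance refreshing as a threat. The likely consequence is an underestimated difference in errors, TDP and TDD. A false benefit is unlikely, because randomisation within centre spreads later participants over both arms.

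The size cannot be derived from the documents. With 10–30% of later controls forewarned and the app arm fixed at 30%, the difference shrinks from 30 points to 27.4–22.1 if they err at 30%, or to 28.7–26.1 if they err at 45%. Two-proportion power falls from 92% to 87–70% or to 90–83% respectively. If the app performs as it did in hospital, the test is hardly affected, but the estimated differences would still be too small. The point justifies inexpensive protection. It does not justify a larger sample or a different primary analysis.

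**What to change.** 1. In section 2.3.5.4, add that each participant signs, with the consent form and before allocation, an undertaking not to disclose the case, drugs or weight to anyone until all sessions at that EMS are finished.
2. In section 2.3.5.1, add to the post-scenario interview one question on whether the participant knew anything of the case beforehand.
3. Record each participant's session number within the EMS week.
4. In section 2.3.14.2, prespecify a supportive sensitivity analysis by session order, for example the arm effect in earlier versus later sessions. Label it as low precision, since there are only about 8 participants per EMS. Report prior knowledge by arm descriptively. Do not exclude participants on it, because the answer is given after allocation is known.

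The session days need not be compressed: that would conflict with the rostering in sections 2.3.5.2 and 2.3.7. The primary analysis and the sample size stay unchanged.

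The cost is one sentence with the consent form, one interview question, one recorded number and one extra analysis. The undertaking does hint that the content matters, but equally in both arms because it is signed before allocation. Prior knowledge has to be asked about on the day, and it cannot be reliably recovered later, so the change should be in place before enrolment starts.

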2.3.6. Outcomes

Primary outcome measures: The primary outcome will be to measure, in each allocation group, the number of medication dosing errors committed during each drug preparation sequence until injection. According to Marcin et al. and Moreira et al, we defined a emergency medication dose administration error as more than 10% deviation from the correct weight dose^{9,12}.

Secondary outcome measures: The secondary outcomes will be to measure, in each allocation group, the followings variables:

A) *Errors that might be encountered during drug preparation*, such as: 1) the amount of drug taken in mL and deviation from the one prescribed on the drug dosing charts or the app, 2) the amount in mL of saline solution taken to dilute the drug, and deviation from the one prescribed, 3) final drug concentration in mg/ml obtained and deviation from the one prescribed, 4) correct or wrong drug chosen by the paramedics compared to the one prescribed on the drug dosing charts or the app (the drugs chosen will be recorded for every participant in order to find any systematic or repetitive error), 5) correct or wrong air purge out of the syringe before injection, 6) correct or wrong labeling of the filled syringe, 7) detection or not of error(s) by the paramedics, 8) stage of error(s) detection: before or after injection, and 9) aseptic errors. These measures of medication errors were selected as they were considered to be the most common sources of medication errors as evidenced in the pediatric medication error literature and meta-analysis^{17,51,52}.

B) *The time points of the drug preparation, in each allocation group*, such as: 1) time in seconds between the end of the drug prescription by the physician and the syringe filled with the drug (TDP), 2) TDP plus time in seconds between TDP and injection (TDD). TDP and TDD are relevant temporal values described in the resuscitation literature^{39,53}.

C) *Questionnaires*: at the end of the scenario, a 6-item questionnaire using a 10-point Likert scale (scored from one to ten to avoid neutral answers) will be provided to the participants. The questionnaire measures (1) the overall stress perceived, (2) the stress perceived during each drug preparation sequence with PedAMINES and with the conventional method(s), and (3) the satisfaction about the preparation method used during the resuscitation scenario. Acceptability and usability testing of the app will be assessed using a 52-item questionnaire based on the unified theory of acceptance and use of technology (UTAUT) model⁵⁴. UTAUT provides a useful tool to assess the likelihood of success for new technology introductions and helps to understand the drivers of its acceptance.

D) *Heart rate (HR) as a stress marker*: a baseline HR before the beginning of the scenario as well as continuous HR monitoring of each participant reflecting his or her stress level will be recorded during the scenario. Mean delta HR values (difference between HR peak values and baseline HR) will be obtained during some small segments of scenario and correlated to the scenario phases and the preparation methods used.

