Consistent with standard emergency medicine practice, we will create resuscitation teams. Two members from the study team, remaining the same along the whole study period, will assist the study participant. A Pediatric Advanced Life Support (PALS) instructor-certified emergency pediatrician will lead the resuscitation, and a nurse playing the role of a second paramedic will assist with resuscitation by performing chest compressions and bag-valve mask ventilation according to the pediatrician instructions, but not drug dose calculation or preparation. Participants will be informed before the scenario starts that these 2 people are study team members. Both study team members will guide each participant through a series of predefined key steps, blinded to the participant, following a standardized resuscitation scenario (see below). The physician will order the medications and allow progression through the scenario only once predefined milestones have been reached, regardless of the occurrence of errors or time to achieve them. The study-specific training and standardization of both study team members is ensured through their involvement in the pilot study⁴⁷ and previous SNSF study and by following the predefined scenario. A certified technician will operate the simulator.

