hypoglycemia” and prompts the participant to prepare and inject an IV bolus of dextrose 10%. Return of a state of consciousness ensues with normal vital signs, but a wide QRS on EKG-monitoring. The physician says: “This child needs an IV bolus of sodium bicarbonate 1 mEq/kg”. As soon as this last medication is administered, the physician asks for transport and the scenario ends. The cameras and the watch are turned off 1 minute later. The measured deviation between the amount of drug delivered and the actual prescribed dose will be measured by the amount of drug in the syringe. As everything is video-recorded, we will be able to verify and measure the exact amount of drug and concentration in the syringe after the scenario. During the whole scenario, the physician, the confederate paramedic and the operator will maintain a stressful resuscitation atmosphere (monitoring alarms are on, the primary assessment (ABCDE) is often repeated, vital signs are frequently reported aloud and the father repeatedly verbalizes his dismay).

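### Is the primary outcome left without a reference dose because one scripted drug order states none?

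*Combined protocol and SAP*

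**What the plan says.** Section 2.3.6 (Outcomes) sets the scoring rule for the primary outcome: "we defined a emergency medication dose administration error as more than 10% deviation from the correct weight dose". Section 2.3.14.1 uses the same idea of a correct weight-based dose for the secondary analysis of deviations. Neither section tabulates that dose for the four drugs.

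Section 2.3.5.1 describes the scenario. The weight is announced at the start: "Here is Junior, a 12-kg, 1 and a half year old boy who suddenly collapsed 15 minutes ago". On ordering, it says: "The physician will order the medications and allow progression through the scenario only once predefined milestones have been reached". The four orders are presented in different ways:

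- Epinephrine is narrated: "a bolus of epinephrine is ordered by the physician and the timed scenario begins". The text ties this order to a cited cardiac arrest algorithm.
- Midazolam is given as speech: "This patient needs an IV bolus of midazolam right now". No dose is stated.
- Dextrose is narrated: the physician "prompts the participant to prepare and inject an IV bolus of dextrose 10"%. This gives a concentration but no dose.
- Sodium bicarbonate is given as speech, with a dose of 1 mEq/kg.

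After the scenario, "the paramedic will be required to recall and describe precisely how he prepared the drugs". The purpose is to confirm that "the drug names and original doses prescribed by the physician were correctly understood". The same section says that the deviation is measured against the dose actually prescribed, using the syringe contents, which can be verified on video.

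**The concern.** A 10% band needs a single centre, and the documents print one for bicarbonate only. The recall check and the measurement sentence presuppose a prescribed dose, yet the quoted midazolam order has none. Section 2.3.1 adds that EMS providers count as prescribers when medication errors are studied, and section 2.3.3 says that a chart user begins by choosing the mg/kg dosage. Read together, these passages seem to disagree on who sets the dose behind the primary outcome.

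If that were so, the drugs would set different tasks. With a spoken dose, an error is one of preparation, as the primary objective in section 2.3.2 has it. Without one, it may also be an error of dose choice, and the time spent choosing falls within the time to drug preparation, whose clock starts when the order ends. The primary model in section 2.3.14.1 pools all four drugs into one method effect. A reference settled only after the data were seen would also be unwelcome, because the video reviewers know the arm (section 2.3.11.1).

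**Working it through.** **How much of the outcome is touched.** Section 2.3.8 gives 120 paramedics, 60 per arm, and section 1 gives 4 drugs each: 120 × 4 = 480 preparations, 120 per drug.

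| Drug | Order as printed | Dose in the order | Preparations |
|---|---|---|---|
| Epinephrine | narrated, algorithm cited | not known | 120 |
| Midazolam | speech | none | 120 |
| Dextrose 10% | narrated | not known | 120 |
| Sodium bicarbonate | speech | 1 mEq/kg | 120 |

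The demonstrated gap is 120/480 = 25%. Adding the two narrated orders gives 360/480 = 75%, but that counts what a funding application happens to print. It does not show that those preparations cannot be scored.

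**Does the rule work once a value is entered?** For bicarbonate, taking the ordered figure as the reference: 1 mEq/kg × 12 kg = 12 mEq. The no-error band runs from 0.90 × 12 = 10.8 to 1.10 × 12 = 13.2 mEq. The other drugs need only one number each.

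**Who sets the dose in the scenario?** Three operational passages point to the physician: the ordering sentence, the recall check, and the definition of time to drug preparation in section 2.3.6, which starts at the end of the physician's prescription. Section 2.3.1 explains the choice of comparator by the autonomy of Swiss EMS. Section 2.3.3 explains how a chart is read, and choosing a mg/kg row is compatible with looking up an ordered dose. Neither says that the paramedic sets the dose in this simulation.

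**What turns on a spoken dose?** The primary reference is the correct dose for a known weight. Speaking it or leaving it out changes the paramedic's task but not that reference. The recall is a comprehension check, not the scoring rule.

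**What would be at stake if the reference were badly placed.** First, the plan's own sample size, for 60% against 30%, two-sided 0.05, 90% power, pooled variance (mean proportion 0.45):

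n = [1.960 × √(2 × 0.45 × 0.55) + 1.282 × √(0.60 × 0.40 + 0.30 × 0.70)]² / 0.30² = 55.7, so 56 per arm, as stated. Power at 60 per arm is 92.1%.

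Now let m be the share of correct preparations wrongly scored as errors. The documents give no value, so m is an assumption. With the same m in both arms, the rates become 0.60 + 0.40m and 0.30 + 0.70m, and the difference is 0.30 × (1 − m).

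| m (assumed) | Difference, both arms affected | Power, 60 per arm | Difference, control arm only |
|---|---|---|---|
| 0 | 30 points | 92.1% | 30 points |
| 5% | 28.5 | 88.8% | 32 |
| 10% | 27 | 85.0% | 34 |
| 20% | 24 | 76.1% | 38 |
| 30% | 21 | 66.0% | 42 |

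Like the sample size, this treats the outcome as one proportion per paramedic. It shows that a poor reference, if kept, would matter. It does not show that the plan leads to one: nothing in the documents puts m above zero, and a misplaced reference can be corrected by rescoring.

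**The case for a change.** The strongest case is that rescoring repairs the score but not the session. Participants act on the words they hear, so the wording of the orders must be settled before the first paramedic starts. That is right, and it is a matter of script preparation. Section 2.4 sets aside two months for preparation before enrolment, and section 2.3.5.1 rests standardization on a predefined scenario run by the same two team members throughout. Both arms hear the same orders, and randomization is stratified by center (section 2.3.10.1).

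A second objection is that the correct dose is not self-evident. Charts cover ranges of doses, methods may differ between EMS (section 2.3.5.4), and the app's drug data can be edited (section 2.2). If a local chart led to a different dose from the reference, control preparations could be scored as errors, as in the last column above. The documents show no such difference. A single reference table applied to both arms, the obvious remedy, would not remove it either: a chart that differed from the table would still produce errors in the control arm.

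Third, the pooled effect may mix preparation with dose choice, and adjusting for drug type does not say which task it describes. That stands as a remark on interpretation. Section 2.1 lists faulty recall of doses among the causes of error, however, so capturing dose choice may be intended. Stating every dose would take it out of the test. This is a fair trade-off, and the planned per-drug proportions and times keep the drugs separately visible.

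Fourth, the reviewers are not blinded to arm. Yet they read an amount and a concentration from video, independently of each other, with a third evaluator for disagreements (section 2.3.13). The comparison with a reference is then arithmetic.

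**Conclusion.** The observation is accurate but does not call for a change to the plan. One scripted order, covering 25% of preparations, lacks a dose that the recall check presupposes, and the per-drug values behind the primary definition are not printed. The definition itself names its reference, the patient's weight is fixed, and the operational passages agree that the physician orders the drugs. The missing values are detail that the team would fill in before scoring.

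No bias between arms is shown, and no loss of power can be derived. The sample size reproduces, and the figures for misplaced references rest entirely on an assumed m. The midazolam line and the recall check must be reconciled in the working script. The choice belongs to the sponsor, and no dose is suggested here.

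The conclusion assumes that one reference per drug is listed before scoring and used alike in both arms and at every EMS, and that the recordings let syringe contents be verified as section 2.3.5.1 says. It would need another look if the reference were chosen after results by arm were known.
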